**Study Product:**

UPRIGHT Go App, manufactured by Upright Technologies Ltd., is an app that connects to the device and tracks data and provides feedback from the device.

The Upright Pro is a wearable biofeedback posture trainer.

**Statistical Plan:**

No power analysis will be done, as only one other study has been published using this device. We'll be using 30 participants, as this study had 30 subjects participating in study.

For within subjects, data will be analyzed using paired T-test analysis. For between subjects data will be analyzed using ANOVA. Currently there are no similar studies to determine the sample size, we plan to analyze the outcomes.

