### **Research Question(s)/Hypothesis(es):**

The purpose of the this study is to determine if patients with back pain who use a device that provides a proprioceptive reminder regarding posture (UPRIGHT device) demonstrate improved pain control and self perception of posture over those who receive a brief instruction on posture and an ergonomic handout.

Hypothesis: There will be no difference in back pain score or self perception of posture between those using the UPRIGHT device and those receiving posture/ergonomic instruction alone.

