### **Scientific Abstract:**

Back pain is one of the most common conditions among the adult population (1). There is evidence that individuals with back pain have impaired motor control of trunk muscles and delayed neuromuscular recruitment (2,3). Poor posture has been associated with spinal extensor weakness, back pain, and lower quality of life scores (4). Those who spend prolonged time sitting in poor posture often develop muscular imbalances leading to tight chest muscles and weakness in back muscles. Back pain is commonly treated with flexibility and strengthening and exercises as well and a health education regarding proper posture (5). The purpose of the this study is to determine if patients with back pain who use a device that provides a proprioceptive reminder regarding posture (UPRIGHT device) demonstrate improved pain control and self perception of posture over those who receive a brief instruction on posture and an ergonomic handout.

Hypothesis: There will be no difference in back pain score or self perception of posture between those using the UPRIGHT device and those receiving posture/ergonomic instruction alone. This is a randomized controlled study to determine if patients between the ages of 18-50, with posture related low back pain, who use the UPRIGHT device demonstrate improved pain control and self perception of posture compared to those given standard ergonomic instruction. Subjects will complete a baseline history, physical exam and questionnaire to assess current pain level.

Subjects will be randomized into two groups. One group will receive the UPRIGHT device and a 15 minute tutorial on using the device. Subjects will complete a 4 week training program using the device. The control group will receive a 15 minute instruction on proper posture and an ergonomic handout explaining how to sit and stand with proper posture. At the end of 4 weeks subjects will be contacted via telephone to complete a questionnaire to assess their current pain level, perception of posture, and satisfaction with the device.

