#### **Study Population:**

A total of up to 45 participants will be enrolled into this study with a target accrual of 35 participants treated.

This study consists of two groups:

1. Upright posture device x 4 weeks.
2. Ergonomic instruction (15-20 min) and handout.

The Inclusion Criteria is as follows:

1. Ages 18-50
2. Postural related back pain

The Exclusion Criteria is as follows:

1. A diagnosis of significant scoliosis, herniated/bulging disc, lumbar spondylolysis, radiculitis, facet arthrosis, fibromyalgia, rheumatoid arthritis, seronegative spondyloarthropathy
2. Neurologic deficits on exam
3. Currently in PT

The participants will fall in either one of the following Intervention /exposure groups: Group 1- Upright device training x 4 weeks Group 2- Ergonomic training 30 min, ergonomic handout. The control group will get the upright device if they still have pain.

Randomization will be done by research member not in contact with participant using [www.randomization.com](http://www.randomization.com) and will use 3 blocks of 10 for randomization. At the end of 4 weeks patient will be reassessed with visual analog pain scale, and self perception posture scale. Patients receiving the upright device will have a brief training on the use of the device and proper posture. They will use a training protocol (attached). The control group will have a 15-20 minute instruction on proper posture and an ergonomic handout.

Patients will be identified by a physician at student health and enrolled by the research team. Informed consent will be obtained.

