#### **Study Procedures:**

Subjects with complaints of back pain will be recruited from Columbia University Student Health and from Columbia Doctors Physical Medicine and Rehabilitation practice. Subjects will be consented and randomized to either the UPRIGHT device group or control group. The UPRIGHT group will get a brief training on how to use the device. This will involve downloading the app on subjects phone. We will set

up a separate de-identified gmail account which will be used collect data from the device. They will be instructed on how and where to attach the device to their back. The subject will be asked to sit with proper posture in a chair without leaning against the back rest with both feet flat on the ground. The training is once daily and each day the time increase according to the provided training protocol. The subjects will wear the device once per day for 4 weeks.

The subject needs to use a new adhesive (which will be provided) each time they put the device on. The device will be calibrated to detect changes in posture. A detailed physical exam as well as medical history, family history will be conducted on all participants. Subjects will then be given a 4 week training protocol through the app. The control group will have a 15 minute instruction on proper posture and an ergonomic handout explaining how to sit and stand with proper posture.

At the end of 4 weeks subjects will be contacted via telephone to complete a questionnaire to assess their current pain level, perception of posture, and satisfaction with the device. At the end of 4 weeks participants in the control group will be given an UPRIGHT device if they continue to have pain.

Prior to recruitment we will pilot the use of this device with 5 healthy controls. The purpose of the pilot study is to assess for any difficulties we may encounter with the device and while training with the device.

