**Recruitment:**

Patients will be identified by a physician at student health or by a Columbia Doctors PM&R physician who will first introduce the study to the patients and enrolled by the research team. Informed consent will be obtained. Subjects who presents to the Columbia Health Clinic or Columbia Doctors Rehabilitation Medicine with complaints of back pain who meet the criteria will be asked to participate in our study. Information about the study will be provided and if they choose to participate they will be consented by our research coordinator. They will then be scheduled for study assessments. This study is completely voluntary. None of residents, students, fellows or employees within our Rehabilitation Department will be asked to participate in this study. Recruitment flyers will also be placed in the Department of Rehab at CUMC as well as displayed at student health at Columbia University.

An electronic flyer (attached) will be sent to the graduate school of arts and sciences communication department for them to attach to their monthly newsletter sent to the graduate students on our behalf. The communication department will not give us their list serve at any time. Graduate students are added to this list serve when registered for graduate classes at Columbia University and the communications department is the sole owner of this list. An individual who wants to participate in the study will contact [name] directly and no one from the communication department will ever see this information.

[name], an employee of Upright, will send out the attached email (Upright\_email script) to individuals who have purchased an Upright device in the past on our behalf. We will never have access to these individuals' contact information or listserve. When someone purchases an Upright device they are added onto their mailing listserve and agree to receive emails from Upright. [name] and Upright will be sending the email referencing our study and provide our contact information. An individual who wants to participate in the study will contact [name] directly and no one from Upright will ever see this information.

**Title:** Upright Back Posture Device Study (AAAR4123)

**NCT:** NCT03769246

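### The between-arm ANOVA does not say which form of the pain score it tests and names no baseline covariate; ANCOVA on the week-4 score would settle both at little cost

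*Combined protocol and SAP*

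**What the plan says.** The hypothesis, under Research Question(s)/Hypothesis(es), compares the arms: "There will be no difference in back pain score or self perception of posture between those using the UPRIGHT device" and those given instruction alone. Under Study Population the outcomes are named: "At the end of 4 weeks patient will be reassessed with visual analog pain scale, and self perception posture scale".

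The Statistical Plan has two method sentences. One is "For within subjects, data will be analyzed using paired T-test analysis"; the other is "For between subjects data will be analyzed using ANOVA". Only the second can test the hypothesis. It gives no response variable and no covariate, and no other section supplies them.

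A baseline pain value is planned. The Scientific Abstract says: "Subjects will complete a baseline history, physical exam and questionnaire to assess current pain level". The paired t-test could not be run without one.

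**The concern.** With two arms, ANOVA reduces to a t-test, and the sentence allows at least two different ones. If the response is the week-4 score, baseline pain plays no part. If it is the change from baseline, or the group-by-time term of a repeated-measures ANOVA (the same test with two time points), baseline enters with its slope fixed at 1. ANCOVA estimates that slope from the data.

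Two things are at stake. The first is precision, which is scarce with about 30 people. The second is that the form is left open: the two readings can give different answers on the same data, and the plan does not say which one counts.

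**Working it through.** **Inputs from the documents.** The Statistical Plan gives N = 30. Study Population gives two arms and 3 blocks of 10, which also makes 30. The 30 is taken from an earlier device study and not calculated, so there is no sample-size figure to reproduce.

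**Assumptions, because the documents are silent.** 15 per arm, two-sided 0.05, complete data. Rho, the SD ratio k (baseline SD divided by week-4 SD) and the effect size are varied. Effects are in week-4 SDs.

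**Variance of the arm difference**, in units of 2 × SD² / n:

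- Week-4 score: 1, on 28 df.
- Change: 1 + k² − 2·k·rho, on 28 df. With k = 1 this is 2(1 − rho).
- ANCOVA: (1 − rho²) × (1 + 1/(N − 4)) = (1 − rho²) × 27/26, on 27 df. The factor 27/26 = 1.038 is the expected cost of estimating the slope.

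**ANCOVA against the week-4 score.** ANCOVA wins when (1 − rho²) × 27/26 < 1, that is rho > sqrt(1/27) = 0.192. At rho 0.5 its variance is 0.75 × 1.038 = 0.779, or 22% lower. Power from the noncentral t:

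| rho | effect | week-4 score | ANCOVA |
|---|---|---|---|
| 0 | 0.8 SD | 56.2% | 54.5% |
| 0.3 | 0.8 SD | 56.2% | 58.4% |
| 0.5 | 0.8 SD | 56.2% | 66.8% |
| 0.7 | 0.8 SD | 56.2% | 82.7% |
| 0.5 | 0.5 SD | 26.2% | 32.2% |
| 0.5 | 0.3 SD | 12.5% | 14.6% |

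At rho 0.5 the 95% CI half-width falls from 0.748 to 0.661 SD.

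**ANCOVA against change, at rho 0.5.** ANCOVA stays at 0.779; change depends on k:

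| k | change variance | ANCOVA relative to change |
|---|---|---|
| 1 | 1 + 1 − 1 = 1.00 | 22% lower |
| 0.8 | 1 + 0.64 − 0.8 = 0.84 | 7% lower |
| 0.7 | 1 + 0.49 − 0.7 = 0.79 | 1% lower |
| 0.6 | 1 + 0.36 − 0.6 = 0.76 | about 2% higher |

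With k = 1, change is the more precise only above rho = 25/27 = 0.926. With k = 0.8 it is slightly more precise for rho of about 0.65 to 0.89, and with k = 0.7 for about 0.53 to 0.81. At the ratios tried of 1.1 and above it never is.

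**Worst case for ANCOVA.** Subtracting b × baseline with any fixed b gives variance 1 + b²k² − 2·b·k·rho, whose minimum, at b = rho/k, is 1 − rho². The week-4 score (b = 0) and change (b = 1) are both fixed-b choices, so neither can go below 1 − rho². ANCOVA's expected variance is therefore at most 27/26 of the better one, 3.8% more, for any rho and k. In power that is about 2 points or less (54.5% against 56.2% at rho 0 and 0.8 SD). A wrong fixed choice can cost far more: with k = 1 and rho 0, change has 32.2% power at 0.8 SD.

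**Type I error.** In simulation with no true effect (k = 1, rho 0 to 0.7), the week-4 and change tests each reject in about 5% of trials. At least one of them rejects in 8.4% to 9.4%.

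**The case against.** The strongest reply is that the gain is modest and partly hypothetical. Much of that stands. At rho 0.3 ANCOVA gains only about 2 points of power over the week-4 score at 0.8 SD, and it does not rescue power at 0.5 SD or below. Against change the gain can vanish: the trial enrols only people with back pain, which could narrow the baseline spread and push k below 1, though the documents do not establish this.

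Three stronger readings are tempting, and the documents do not support them.

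- *The plan ignores baseline pain.* That is true only if the response is the week-4 score. Under change or group-by-time, baseline enters the response.
- *ANCOVA beats both forms by 22%, or for every rho between about 0.19 and 0.93.* The two limits belong to different comparators, and the 22% against change and the upper limit both need equal SDs, which are not given.
- *The test has an inflated error rate.* Either form, fixed in advance, holds 5%. The 8–9% would apply only if the form were picked after seeing the data, and nothing in the plan says that it will be.

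What survives is that the response is unspecified, and that ANCOVA has a small bounded cost while either ANOVA form can be a poor choice.

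**Conclusion.** The point holds as a cheap improvement. The only sentence that tests the trial's hypothesis leaves its response open and names no covariate. That gap is certain from the text. The size of the gain is not, because rho and the SD ratio are unknown. On 15 per arm and two-sided 0.05, ANCOVA at rho 0.5 has 22% lower variance than the week-4 score, and anything from 22% lower to about 2% higher than change over SD ratios of 1 down to 0.6.

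A reader might infer bias or a faulty test; neither follows. The adjustment is also secure for pain only, since the baseline questionnaire is described as covering pain, and a baseline posture score is at most implied by the word for reassessment at week 4.

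**What to change.** Replace the between-subjects sentence with:

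> The arms will be compared on the week-4 VAS pain score by ANCOVA with baseline pain, measured before randomisation on the same scale, as covariate; the adjusted difference will be reported with a two-sided 95% CI. Self perception of posture will be analysed the same way if a baseline score is collected, otherwise on the week-4 score. The between-arm comparison tests the stated hypothesis; within-arm paired t-tests are descriptive.

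First confirm that baseline pain is recorded before randomisation and on the same VAS. The Scientific Abstract does not name the baseline scale. Study Procedures says "Subjects will be consented and randomized to either the UPRIGHT device group or control group" without placing the questionnaire, and Recruitment says only, after consent, "They will then be scheduled for study assessments". Confirm too whether a baseline posture score exists.

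The cost is 1 df and up to about 4% variance inflation. If those confirmations hold, no new data are needed for pain.
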